2.0 Study aims and outcome measures

Specific Aim 1: Localize neural effects of dlPFC TBS We will show that persisting neural changes induced by TBS to the dlPFC will affect the FPN. We predict that TBS alone (subjects not performing a cognitive task), compared to vertex stimulation, will increase fMRI activation in the FPN during the n-back and increase FPN connectivity during resting state BOLD. We also predict that TBS will increase resting perfusion in the FPN. Exploratory analyses will search for regions outside the FPN that change with stimulation to develop a comprehensive picture of how TBS to the dlPFC interacts with brain networks.

Specific Aim 2: Demonstrate modulation of the effect of dlPFC TBS by a cognitive task We predict that FPN changes during iTBS administered while subjects perform the n-back task will be greater than when they are not performing a task. We will also test the same hypothesis for BOLD resting state connectivity, and ASL-measured perfusion, in addition to exploratory hypotheses on brain networks outside the FPN.

Primary outcome measures for Aims 1 & 2:

- 1) 2-back minus 1-back BOLD activation, voxelwise in FPN
- 2) FPN connectivity to dlPFC TBS stimulation target
- 3) rCBF at stimulation target

Secondary outcome measures for Aims 1 & 2:

- 1) 2-back minus 1-back BOLD activation, voxelwise in whole brain
- 2) rCBF in FPN

Specific Aim 3: Demonstrate improvement in cognitive control with TBS, modulated by cognitive task during stimulation We will test predictions that n-back performance will improve following TBS to dlPFC, but not vertex, and will improve even more following TBS during n-back performance. Exploratory analyses will examine correlations between performance changes and network changes, suggesting mechanistic connections between TBS and performance changes.

Primary outcome measure for Aim 3: accuracy to 2-back

[figure not shown]
Secondary outcome measures for Aim 3: d-prime, reaction time

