4.0 Study Participants

4.1 Participants inclusion/exclusion criteria

Participants will be healthy individuals, ages 18-50. The upper limit of 50 will reduce variance from older subjects, who exhibit less specific activation patterns.(63, 64) We will recruit ~60 individuals (50% women) to allow for drop-outs and subjects who cannot tolerate TBS, aiming for 40 subjects in the final analysis.

Inclusion/exclusion criteria: (1) No history of past or current mental illness (except for simple phobias), but prior h/o substance dependence OK if in remission for greater than 5 years; (2) Not taking any medication, prescription or non-prescription, with psychotropic effects (birth control medications allowed); (3) No first-degree family members with a history of epilepsy; (4) Age 18 –50; (5) If a woman of child bearing age, not pregnant or trying to become pregnant; (6) No history of serious neurological illness (including, but not limited to, seizures/epilepsy) or current medical condition that could compromise brain function, such as liver failure; (7) No history of closed head injury, e. g. loss of consciousness > ~5 min, hospitalization, neurological sequela; (8) Ability to tolerate small, enclosed spaces without anxiety; (9) No family history of epilepsy in first degree relatives; (10) No metals, implants or metallic substances within or on the body that might cause adverse effects to the subject in a strong magnetic field, or interfere with image acquisition, e. g. aneurysm clips, retained particles (e.g. metal workers with exposures), neurostimulators, foil-backed transdermal patches, carotid or cerebral stents, CSF shunts; magnetic dental implants, ferromagnetic ocular implants, pacemakers, automatic implantable defibrillators; (11) Size compatible with scanner gantry, e. g. men over 6 feet tall that weigh more than 250 lbs, men under 6 feet tall that weigh over 220 lbs, women over 5'11" tall that weigh more than 220 lbs, or women under 5'10" tall that weigh more than 200 lbs. Subjects of these weights or greater typically have difficult fitting into the fMRI scanner properly; (12) Ability and willingness to give informed consent to participate.

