4.4 Intervention assignment procedures

All subjects will receive all interventions in a cross-over design. The three intervention sessions (visits 3, 4 & 5) will be given in counter-balanced order, stratified by gender. Subjects will be blind to the nature of the questions being asked; however, they will be told that different stimulation paradigms will be used, which will be evident to the subjects as they go through the procedures.

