6.3 Visits 3,4,5, Combined TMS/MRI sessions

These sessions involve the experimental manipulation, using iTBS TMS prior to the MRI session, in order to test hypotheses described in the Aims. These visits will also occur at the fMRI laboratory, which houses the TMS suite, across the hall from the MRI magnet. Each TMS session will differ, depending upon how iTBS is delivered and what the subject is doing while receiving stimulation. The MRI sessions will be identical.

We will seek to test participants at the same time of day to reduce circadian variability, separated by 1 to ~4 days. We will also work to schedule the 3 sessions in the same week, avoiding Monday. Each session will last approximately 2-3 hours. Below, we describe what happens for each of the three visits.

6.3.1 Safety assessment: We will review the subject's safety screening forms for fMRI and TMS to make sure nothing has changed since the prior session. We will also record sleep and ingestions of psychoactive substances (caffeine, alcohol, nicotine). We will prepare them for the MRI scan, ensuring that they remove all metal from their person (lockers are provided at the fMRI laboratory to store personal items such as wallets, cell phones).

6.3.2 Neuronavigation for TBS sessions: To determine the site for stimulation, we will use neuronavigation, with structural and functional information to account for individual variability in recruitment of the FPN. BOLD mages acquired from the first MRI session (Visit #2) will be analyzed with standard methods to determine the activation of 2-back minus 1-back, and aligned with the subject's high resolution SPGR structural scan. These data will be transferred to the Brainsight Frameless system (Rogue Research, Montreal CA). For the dlPFC target, we will locate the junction of the anterior and middle third of the left middle frontal gyrus (MFG), which corresponds to Brodmann area 46,(78, 79), and within a zone that is 1/3 the length of the MFG, will search for the locus of greatest activation in BOLD activation (2-back minus 1-back, or 1-back minus 2-back) for each subject, using those coordinates as the site of stimulation. The Brainsight system will be used to identify the overlaying scalp position. For the vertex (control) target, we will locate the approximate vertex, according to standard 10-20 system, but in a region where no BOLD change is detected.

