Exploratory analysis, amplitude of low frequency fluctuations (ALFF): ALFF, and fractional ALFF (fALFF), measures the magnitude of low frequency BOLD fluctuations, generally from 0.01 to 0.1 Hz.(99) fALFF measures the fractional strength (relative to the full spectrum) of BOLD fluctuations. ALFF is correlated with CBF,(100, 101) so this measure provides an alternative to supplement the pCASL analysis. This is a potentially important measure for brain stimulation, as fALFF/ALFF abnormalities have been reported in psychiatric disorders,(102-104) and fALFF in the subgenual cingulate gyrus has been shown to predict response to electroconvulsive therapy.(105) This analysis will use the BOLD resting data as above, except that frame censoring (scrubbing) will not be performed, since censoring can affect the frequencies in a run of BOLD-acquired MRI data. Each voxel's BOLD time series will be transformed into the frequency domain and the mean amplitude of the spectrum over the frequency range of 0.01–0.1 Hz will determine ALFF. fALFF for two bands (slow-4; 0.027-0.073 Hz; and slow-5, 0.01-0.027 Hz) will be calculated as the magnitude for that band over the magnitude of the full spectrum. This analysis will focus on the 10 mm diameter sphere under the site of stimulation. Alpha level for this analysis will be set at 0.017 (0.05/3), two-tailed.

Exploratory analyses, between measures: Exploratory analyses will also test for correlations between the three MRI measures, to provide a richer picture of iTBS effects. Lastly, we recognize that vertex stimulation, here being used as a control condition for dlPFC stimulation, may have some effects on brain networks, although it was selected to avoid the FPN. With some caveats (effect of order, since baseline is not counter-balanced), we can use baseline measures from the first MRI session (no preceding TMS session), to see if iTBS differences represent a change in the dlPFC-stimulated condition or the vertex-stimulated condition. An additional exploratory analysis will compare stimulation over the 'activated target' (2-back minus 1-back) versus the 'deactivated target' (1-back minus 2-back), based on how the target was selected.

Specific Aim 2: Demonstrate modulation of the effect of dlPFC iTBS by a cognitive task

Primary outcome measures:

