Analysis plan: For analysis of n-back performance, our primary performance measure will be accuracy to the 2-back condition. Secondary measures will be d-prime, to capture the sensitivity to the target and not bias to respond, and median reaction time. Although we found significant effects on d-prime for our list learning paradigm, that memory task was very different from the more demanding n-back, which requires updating and manipulation in short-term storage, while our list learning task involved only incidental memory. For each measure, we will conduct a repeated measures ANCOVA, with the performance measure across the three iTBS conditions as the repeated measure, and sex as a fixed, between-subject factor and age as a co-variate. Post-hoc, paired t-tests will be used for specific contrasts.

(H3.1) 2-back accuracy will be greater for dlPFC stimulation (no task during iTBS) relative to vertex stimulation

(H3.2) 2-back accuracy will be greater for dlPFC stimulation applied while subjects carry out an n-back during iTBS stimulation during stimulation, compared to when they receive stimulation alone. The same hypotheses will be applied to d-prime, our secondary measure. Two-sided tests will be used, because it is also possible that performance may worsen, either with stimulation alone, or when combined with subjects performing the n-back. It would be critical to know, for example, that performance of a cognitive control task was degraded by combining TMS with a task. Although a commercial device is being tested on dementia patients, relying on the assumption that the combination is beneficial,(18) we are not aware of this assumption being tested as we propose to do here.

Exploratory analyses around performance correlations: In addition to testing questions about performance, we will also examine correlations between performance and the MRI measures from Aims 1 and 2, testing important questions around mechanism. Since we will systematically test for correlations between both performance measures and the three primary measures from each aim (18 correlations), alpha will be set at $0.05/18 = 0.0028$.

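### The exploratory performance-by-MRI correlations have no visit adjustment, so drift over visits 3–5 that affects both measures can create, inflate or mask a correlation, mainly for n-back activation

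*Combined protocol and SAP*

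**What the plan says.** Section 8.0, under Specific Aim 3, states of the exploratory analyses that "we will also examine correlations between performance and the MRI measures from Aims 1 and 2, testing important questions around mechanism". It continues: "Since we will systematically test for correlations between both performance measures and the three primary measures from each aim", with the threshold set at 0.05/18. Section 2.0 says what is correlated and how it will be read: "Exploratory analyses will examine correlations between performance changes and network changes, suggesting mechanistic connections between TBS and performance changes".

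On design, section 4.4 states: "The three intervention sessions (visits 3, 4 & 5) will be given in counter-balanced order, stratified by gender". Section 6.3 (Visits 3,4,5) has these sessions "separated by 1 to ~4 days", with the same scan protocol, including the n-back, each time. Section 4.1 is "aiming for 40 subjects in the final analysis".

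No analysis of visits 3–5 contains a visit, period or order term. The performance ANCOVA has iTBS condition, sex and age. The session comparisons of the three primary MRI measures are one-sample or paired t-tests. The first-level BOLD model has a session regressor, but that term works within a subject's time series and does not remove visit position from a between-subject difference score. Section 8.0 raises order only as a caveat to the comparison with baseline. Under Aim 1 it adds: "Exploratory analyses will also test for correlations between the three MRI measures, to provide a richer picture of iTBS effects", without saying whether levels or session differences are meant.

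**The concern.** In a counterbalanced crossover it is natural to assume that visit effects have been dealt with. They have been for the mean of each contrast, because the visit gap averages to zero. A correlation between two contrasts is different: it uses the spread of the differences across subjects, and counterbalancing is what makes the gap vary. One subject has dlPFC two visits after vertex, another two visits before. Whatever that gap adds to the accuracy difference and to the activation difference, the size and sign of the gap are common to both.

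At stake is the reading of the correlations the plan offers as pointers to mechanism. A shared trend can produce a correlation when iTBS does nothing. Trends of the same sign inflate a true positive link, and trends of opposite sign (for example accuracy rising and activation falling with practice) can hide one. The Bonferroni threshold does not help, because it allows for the number of tests and not for a bias common to both variables.

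**Working it through.** **Inputs from the documents.** Threshold 0.05/18 (section 8.0); 40 analysable subjects (section 4.1); three conditions counterbalanced over visits 3–5 (section 4.4); difference scores as the correlated quantities (section 2.0).

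**Inputs assumed.** The documents give no practice slopes or SDs. Slopes b are in SDs of the trend-free difference score per visit. There is no iTBS effect and no true link unless stated. Subjects are spread as evenly as possible over six orders.

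**The plan's figure.** 0.05/18 = 0.00278, which rounds to 0.0028 and reproduces. With n = 40 this needs |r| of about 0.46. Separately from this point, two performance measures × three MRI measures × two aims is 12, whereas 18 needs three performance measures (3 × 3 × 2). I keep the stated 18.

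**Formula.** Let g be the visit position of one condition minus that of the other. Then d_perf = effect + b1·g + error and d_MRI = effect + b2·g + error, with the same g. Over six orders g takes the values 1, 2, −1, −2, 1, −1: mean 0, variance 12/6 = 2. A three-order Latin square (1, −2, 1) also gives mean 0 and variance 6/3 = 2. The induced correlation is

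ρ = 2·b1·b2 / √[(1 + 2·b1²)(1 + 2·b2²)].

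At 0.1 in both: 0.02/1.02 = 0.02. At 0.2: 0.08/1.08 = 0.07. At 0.3: 0.18/1.18 = 0.15. At 0.5: 0.50/1.50 = 0.33. With b2 = 0, ρ = 0.

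**Simulation.** 40,000 replicates per scenario, two-sided test at 0.05/18. Ranges cover repeat runs; they differ partly in where the four subjects left over from six equal groups fall.

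| Slopes per visit (performance, MRI) | ρ | False positives, as planned | Adjusted for three-level visit |
|---|---|---|---|
| 0, 0 | 0 | 0.26–0.27% | 0.27% |
| 0.1, 0.1 | 0.02 | 0.25–0.31% | 0.29% |
| 0.2, ±0.2 | ±0.07 | 0.5–0.6% | 0.26–0.27% |
| 0.3, ±0.3 | ±0.15 | 1.7–2.1% | 0.27% |
| 0.5, −0.3 | −0.23 | 5.0–5.5% | 0.27% |
| 0.5, ±0.5 | ±0.33 | 17.5–20% | 0.26–0.27% |
| 0.5, 0 | 0 | 0.24–0.27% | 0.27% |

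**Practice that levels off.** Put the whole gain between visits 3 and 4. The gap's contribution then has variance (2/3)s² for a step of s. A step of 0.5 in both measures gives ρ = 0.167/1.167 = 0.14 and about 1.7% false positives. A step of 0.7 gives ρ = 0.327/1.327 = 0.25 and about 7.5%. For the 0.7 step, a single linear gap term leaves r of about 0.08 and 0.5–0.7%; the three-level visit term returns the rate to about 0.3%.

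**With a true correlation of 0.5.**
- No trend: power 64% as planned, 62% with the linear gap, about 60–61% with three-level visit, about 55% with six-level order.
- Slopes +0.3/−0.3: 7–8% as planned, about 60–61% with three-level visit.
- Slopes +0.3/+0.3: 85–86% as planned, which is inflated; about 60% with three-level visit.

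**If levels are meant.** Correlating post-session levels within a condition does not avoid the problem: visit position still varies between subjects, with variance 2/3.

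**The case against.** The case against an alarming reading is strong, and most of it stands.

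- **Status.** Both sections call these analyses exploratory, and section 2.0 speaks only of suggesting connections. No primary or secondary outcome depends on them.
- **Scope.** Both measures must drift. Connectivity and rCBF are resting scans with no task to practise, and the documents give no reason for them to trend. They account for two of the three MRI measures, so 12 of the 18 correlations. For activation, the 2-back minus 1-back contrast is taken within a session, so scanner habituation common to both loads cancels. Task practice remains the plausible source.
- **Size.** The slopes are assumptions. Subjects practise in the mock scanner at screening and do a full n-back scan at visit 2, so the earliest gains fall before the counterbalanced visits. At 0.1 SD per visit there is no inflation. The 0.5 case needs a full SD of change from visit 3 to visit 5 in both measures, and a plateau shrinks it.
- **Quantity correlated.** Difference scores are inferred from section 2.0; section 8.0 does not define them.

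None of this removes the mechanism. Counterbalancing answers a question about means, not covariances, and section 8.0's allowance for slight changes in implementation does not commit to a visit term.

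A reader might infer that all 18 tests are invalid, that the H1–H3 contrasts are biased, or that an artefact will be reported as an iTBS mechanism. The documents support none of these. The mean contrasts stay unbiased, the resting-measure correlations are exposed only under a further assumption, and the stated interpretation is tentative.

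**Conclusion.** The point holds in a conditional form. As planned, the correlations have no protection against a visit trend common to performance and the MRI measure, and 0.0028 is not their error rate if such a trend exists. The concern is concentrated in the correlations with n-back activation, a third of the set (6 of the stated 18), because accuracy and activation come from the same task repeated over a short period. The size cannot be fixed from the documents: it is negligible at about 0.1 SD per visit, roughly double the nominal rate at 0.2, six to seven times at 0.3, and 18–20% in absolute terms at 0.5. These figures rest on 40 subjects, near-even orders, linear trends and equal-sized slopes in both measures. The direction of distortion depends on the signs of the two trends. This is an inexpensive improvement to an exploratory analysis and not a threat to the primary results.

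**What to change.** In section 8.0, under the Aim 3 performance correlations, state that the correlated quantities are session differences and name the two sessions contrasted. Replace the simple correlations with partial correlations adjusted for visit as a three-level factor: for each subject, include the differences in the visit indicators between the two contrasted sessions. Report the unadjusted value alongside. Apply the same adjustment to the between-measure correlations under Aim 1 if those use session differences.

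The cost is a sentence or two of text, the visit order already recorded, and 2 degrees of freedom: about 3 to 4 points of power at a true correlation of 0.5 when there is no trend. The alternatives are less suitable. A linear gap term costs 1 degree of freedom and about 2 points, but leaves some bias if practice plateaus. Six-level assigned order costs 5 degrees of freedom and about 9 points.

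The adjustment removes the average visit trend only. If fast learners change more on both measures, that correlation remains, and the report should say so.

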9.0 Ethics and Protection of Human Subjects

9.1 Ethical Standard and IRB Review

The investigator will ensure that this study is conducted in full conformity with the principles set forth in The Belmont Report: Ethical Principles and Guidelines for the Protection of Human Subjects of Research, as drafted by the US National Commission for the Protection of Human Subjects of Biomedical and Behavioral Research (April 18, 1979) and codified in 45 CFR Part 46 and/or the ICH E6; 62 Federal Regulations 25691 (1997) and the Declaration of Helsinki and Good Clinical Practice (GCP).

All protocol amendments must be IRB approved prior to implementing, except when change is for patient safety.

9.2 Subject Confidentiality

Study staff will make every effort to limit identifiable information on potential subjects during recruitment. The minimum amount of information will be recorded, and staff are alerted to the dangers of printing, faxing and emailing sensitive information. Phone conversations with potential research subjects will occur behind closed doors, and staff will ask callers if they are in a location where sensitive information can be discussed without danger of revealing confidential information. Any information gathered on subjects who prove ineligible will be destroyed as soon as possible (a list of patients who have declined or screened out will be maintained through the recruitment phase in order to avoid contacting these subjects again).

9.3 Potential Risks and Minimization of Risks

9.3.1 Potential Risks

9.3.1.1 Issues around confidentiality and the disclosure of sensitive information:

Subjects will grant the experimenters access to protected health information. They will also reveal sensitive information about themselves, which will include their psychiatric status and any history of substance abuse. Subjects may feel uncomfortable revealing this information, and there is a risk of losing confidentiality. Subjects will also be informed in the consent document that confidentiality will be limited in cases where the subject reveals intentions to harm themselves or others, and the investigator feels that the proper authorities may need to be notified in order to prevent the occurrence of harm to the subject, or others.

9.3.1.2 The risks associated with the MRI study are:

- 1) A minor risk of discomfort or anxiety from being in the confined space of the MRI scanner.
- 2) Fast imaging sequences, such as those employed in this study, have the potential to induce peripheral nerve stimulation (PNS). PNS can be described as a light touching sensation on the skin surface and may cause mild discomfort but is not harmful to the subject.
- 3) Risks of hearing damage due to loud noises produced by the scanner.
- 4) Risk that the magnetic resonance image will reveal a minor or significant lesion in the brain, e. g. a tumor, previously unknown to the subject, and requiring additional follow-up.
- 5) Risk of injury from objects accelerated by the strong magnetic field of the magnet, striking the subject; or metallic substances on the skin or foreign bodies implanted deliberately or accidentally in the subject that acquire kinetic or thermal

energy from the magnetic or radiofrequency emissions of the MRI, causing tissue injury to the subject.

6) Sometimes, subjects report a temporary, slight dizziness or light-headedness when they come out of the scanner.

7) Potential risk for pregnant women: According to the NIMH Council Workgroup on MRI research and Practices (September, 2005), "there is no known risk of MR brain scanning of a pregnant woman to the developing fetus for scanning at 4T or less, and no known mechanism of potential risks under normal operating procedures." Nevertheless, subjects should be warned about potential risks, not yet discovered.

9.3.1.3 The risks associated with TMS:

1) Local scalp pain near stimulation site (common, not serious): Activation of muscles and nerves near the site of stimulation can cause substantial pain and discomfort, depending on the intensity and frequency of stimulation.

2) Headache or neck pain (common, not serious): Headache and neck pain, typically lasting up to a few hours on the day of stimulation, are the most frequent side effects of TMS.

3) Sound exposure (rare, serious): When producing a magnetic pulse train, the stimulating coil produces a series of brief clicks. No evidence of hearing loss has been found in humans exposed to TMS, despite extensive exposure to repeated stimulations over several years.

4) Risk of Seizure Induction (rare, serious): The major safety concern about TMS is the possibility of eliciting a seizure, although TMS has rarely been associated with the induction of seizure, even in patients with epilepsy. For example, a recent international consensus conference rated the risk of seizure inductions during low-frequency rTMS as "rare, and usually protective." Thus, seizure risk, while not zero, is so low as to be difficult to estimate. Even with rTMS therapy for depression, patients are routinely treated on psychotropic medications, and the risk of seizure induction is estimated at 1/30,000 treatments.(7)

5) Syncope (rare, not serious): In the setting of altered sensory stimulation, subjects occasionally experience brief loss of consciousness, usually attributable to vasovagal syncope.

6) For women of child-bearing potential: It is unknown if TMS can pose a risk to fetuses.

